#### **2. For continuous measurements of tumor response (RECIST, percent change in tumor volume and pre-surgery lesion size):**

1. ROC analysis will be used to assess the diagnostic performance of CEDM and mammography. The Area under the ROC curve (AUC) will be compared. A leave-one-out cross validation algorithm will be used to reduce bias from overfitting.
2. The agreement between CEDM and mammography in RECIST, percent change in volume and pre-surgery lesion size will be assessed using intraclass correlation (ICC).

#### **3. Spearman's rank correlation will be used to measure the association between final pathologic and imaging tumor size.**

## **9.0 STUDY MANAGEMENT**

### **9.1 Conflict of Interest**

Any investigator who has a conflict of interest with this study (patent ownership, royalties, or financial gain greater than the minimum allowable by their institution, etc.) must have the conflict reviewed by the UTSW COI Committee and IRB according to UTSW Policy on Conflicts of Interest. All investigators will follow the University conflict of interest policy.

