**STUDY SUMMARY**

Title	Performance of contrast-enhanced spectral mammography to assess neoadjuvant therapy response
Short Title	Contrast-enhanced mammography Assessment of Breast Cancer Neoadjuvant Therapy response
Protocol Number	The standard protocol number used to identify this study
Phase	III
Methodology	Prospective, Single Arm, Unblinded
Study Duration	24 months
Study Center(s)	Single-Center, UTSW Breast Center & Parkland Moody Center for Breast Health
Objectives	
Primary Objectives
 
 
1. To investigate the diagnostic accuracy of Contrast Enhanced Spectral Mammography (CEDM) in predicting early neoadjuvant therapy response and pCR compared to mammography.
 
2. To investigate the correlation accuracy of CEDM pre-operative lesion size and final pathological size, compared to mammography.
 

Number of Subjects	100
Diagnosis and Main Inclusion Criteria	
 
1. 18 years and older male or female patients
 
2. Ipsilateral intact biopsy-proven breast cancer clinical T1-T4 (by imaging)
 
3. Available mammography and ultrasound imaging of the existing index cancer, with orthogonal measurements
 
4. Prior history of ipsilateral or contralateral breast cancer, presenting with a new primary or recurrent disease.
 
5. Patients who were determined to be candidates for either neoadjuvant chemotherapy or neoadjuvant endocrine therapy by the treating physician.
 
6. Women of child-bearing potential and men must agree to use adequate contraception (hormonal or barrier method of birth control; abstinence) prior to study entry, for the duration of study participation, and for days following completion of study participation. Should a woman become pregnant or suspect she is pregnant while participating in this study, she should inform her treating physician immediately.
 

Study Product(s), Dose, Route, Regimen	Contrast-Enhanced Digital Mammography
Duration of administration	N/A
Reference therapy	
Statistical Methodology	Descriptive Statistics will be produced. Spearman rank correlation will be used to measure the agreement between final pathologic and imaging tumor size data. ROC analysis will be used to assess the diagnostic performance of CEDM.

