#### **2.2 Secondary Objectives**

- 2.2.1** To investigate the correlation of CEDM pre-operative lesion size and final pathological size.
- 2.3.1** **2.2.2** To determine additional sites of disease in the ipsilateral or contralateral breast identified by CEDM.

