## **6.3 Pathology**

Final histopathology for correlation will include the size of residual tumor (ypT), tumor cellularity (%) and amount of DCIS (%). Per AJCC8th edition [Amin MB, Edge SB, Greene FL, et al, eds. AJCC Cancer Staging Manual. 8th ed. New York: Springer; 2017] (ypT) is based on the largest continuous focus of residual invasive cancer, if present. Treatment-related fibrosis adjacent to residual invasive carcinoma or between foci of residual cancer is not included in the ypT maximum dimension. When multiple foci of residual tumor are present, the (m) modifier is included.

In addition, we will record ki67 index pre and post therapy and its potential correlation with the degree of tumor response seen on CEDM.

The agreement between pre-operative CEDM measurements and mammography in categorizing tumor response RCB0-I/ RCBII/RCBIII will be assessed using weighed kappa.

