### **8.2 Sample Size and Accrual**

Due to the exploratory nature of the study and lack of reliable prior information, a formal sample size calculation was not done. We are proposing to accrue 100 patients for enhanced certainty of our descriptive statistics. We assume 40% prevalence of pCR. A sample of 100 patients will provide 95% confidence intervals of at most (maximum)  $\pm$  0.17 (for sensitivities),  $\pm$  0.14 (for specificities) and  $\pm$  0.12 (for AUC). Simple asymptotic with continuity correction and normal approximation was used for calculation for sensitivity and specificity. Binormal approximation was used for the calculation for AUC. Assuming one lesion per patient, 100 patients will provide 95% confidence interval of spearman rank correlation of lesion size with a width no larger than 0.39. Fisher's transformation followed by a normal approximation was used for calculation. Results from this study would help us design a multi-institutional study allowing comparison to other imaging modalities with a larger patient cohort.

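### The single size correlation does not say how patients with pCR are handled: entered as zeros they mix pCR detection with sizing, and left out they make the stated 0.39 interval width inapplicable

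*Combined protocol and SAP*

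**What the plan says.** Secondary objective 2.2.1 is "To investigate the correlation of CEDM pre-operative lesion size and final pathological size". The Study Summary lists the same question, compared with mammography, among the primary objectives. The analysis is one sentence, Section 8.3 item 3: "Spearman's rank correlation will be used to measure the association between final pathologic and imaging tumor size". The Study Summary describes it as agreement: "Spearman rank correlation will be used to measure the agreement between final pathologic and imaging tumor size data".

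Section 6.3 defines the pathologic size: ypT "is based on the largest continuous focus of residual invasive cancer, if present". Appendix C classifies a patient with no residual disease as ypT0. Section 6.1 defines complete pathologic response as an RCB of zero, and imaging complete response as the disappearance of all lesions.

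Section 8.2 states "We assume 40% prevalence of pCR". Then, "Assuming one lesion per patient", it says that "100 patients will provide 95% confidence interval of spearman rank correlation of lesion size with a width no larger than 0.39", and adds that "Fisher's transformation followed by a normal approximation was used for calculation".

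No section says whether a patient with pCR enters the size correlation as zero or is omitted, how ties are ranked, or that a separate correlation is planned in patients with residual tumour.

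**The concern.** At the plan's own prevalence, about 40 of 100 patients would have no residual invasive focus to measure. If they enter as zeros, 40% of the pathologic values are tied at the bottom of the ranking. A modality that reads zero in most of those patients and above zero in most others then earns a positive rank correlation, whether or not it orders the residual tumours by size. Recognising pCR is already assessed in Section 8.3 by sensitivity, specificity and AUC, so the size coefficient would partly repeat that result.

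Two conclusions are at stake. CEDM could be reported as sizing residual tumour moderately well on the strength of detecting pCR. In the comparison with mammography that the Study Summary lists, the modality that detects pCR better would show the higher size correlation even if neither could size residual tumour. With no rule written down, the analysis set could also be settled after the data are seen.

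**Working it through.** **Inputs.** N = 100, one lesion per patient, 40% pCR and the Fisher method are from Section 8.2. Mammography sensitivity 54.2% and specificity 86.3% for predicting pCR are from Section 1.2. The documents give no accuracy for CEDM, so the range from 80%/85% to 100%/100% is an assumption. Here sensitivity is the chance that imaging reads zero in a patient with pCR, and specificity is the chance that it reads above zero in a patient with residual tumour.

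**Step 1: reproduce the stated width.** The interval is widest at r = 0, where the width is 2·tanh(1.96/√(n − 3)).
- n = 100: 1.96/√97 = 0.199, so the width is 0.393, matching the stated 0.39.
- n = 60 (100 × 0.60, patients without pCR): 1.96/√57 = 0.260, so the width is 0.508.
- Using variance 1.06/(n − 3) instead gives 0.404 at n = 100, so the plain Fisher form was used.

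The precision statement therefore counts the roughly 40 patients expected to have pCR as sized lesions.

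**Step 2: closed form for zeros with perfect detection.** Let p = 0.40, both sizes be zero in pCR, and the two sizes be unrelated among residual tumours. On a 0-to-1 rank scale, pCR patients sit at mid-rank p/2 = 0.20 and the others average p + (1 − p)/2 = 0.70, a gap of 0.50.
- Between-group part: p(1 − p) × 0.50² = 0.24 × 0.25 = 0.060.
- Within-residual part: (1 − p)³/12 = 0.216/12 = 0.018.
- Pooled Spearman = 0.060/(0.060 + 0.018) = 0.77.

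The same formula gives 0.48, 0.65 and 0.86 at pCR prevalences of 20%, 30% and 50%.

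**Step 3: imperfect detection, by simulation.** Settings: 40% pCR, independent sizes among residual tumours, and missed pCRs given a size from the same distribution as residual tumours.

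| Sensitivity/specificity for pCR | Pooled Spearman | Among residual tumours |
|---|---|---|
| 100%/100% (assumed) | 0.77 | 0 |
| 90%/90% (assumed) | 0.62 | 0 |
| 80%/85% (assumed) | 0.50 | 0 |
| 54.2%/86.3% (Section 1.2, mammography) | 0.30 | 0 |

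In simulated trials of 100 patients, the central 95% of pooled values ran from 0.48 to 0.74 at 90%/90%, and from 0.11 to 0.48 at the mammography figures.

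**Step 4: the reverse direction.** The size correlation among residual tumours is now made strong (underlying correlation 0.7), with residual tumours read as zero on imaging kept in at zero. At the mammography accuracy:
- if the missed tumours are those with the smallest imaging size, the residual-disease correlation is 0.68 and the pooled value 0.57;
- if tumours are missed at random, the values are 0.51 and 0.46.

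Pooling can therefore lower the coefficient as well as raise it.

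**The case against.** The strongest reply is that the all-patient correlation is a legitimate answer to objective 2.2.1. The objective is not limited to residual disease, zero is a real pathologic size, and a lesion measured on CEDM in a patient with pCR is a real overestimate. Before surgery nobody knows who has pCR, and restricting to residual disease selects on the pathology result and discards those overestimates. All of this stands. A reader might infer that the pooled coefficient fails to answer the size objective; the documents do not support that. What they support is that one coefficient cannot separate detection from sizing.

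Pooling is also inferred, not stated. Section 8.3 names no analysis set, and the wording of Section 6.3 fits either a zero or no value in pCR. The evidence for pooling is the n = 100 behind the 0.39. This too stands, but it does not remove the problem: one reading mixes two questions, and the other invalidates the width.

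A reader might further infer that the coefficient is bound to be inflated. Step 4 shows otherwise, and the larger figures rest on CEDM accuracies that the documents do not give. At the only mammographic accuracy documented, the artefact is about 0.30.

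Finally, Section 2.2 makes this a secondary objective, Section 8.2 calls the study exploratory, and Section 8.3 allows further exploratory analyses. That lowers the stakes, but the allowance does not commit anyone to this analysis.

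**Conclusion.** The concern holds in a limited form. The plan gives one size correlation with no rule for patients with pCR, and its precision figure counts them. Entered as zeros, they can produce a coefficient of about 0.30 (mammography accuracy) to between 0.50 and 0.77 (assumed CEDM accuracies) with no ability to size residual tumour. With good sizing and poor detection, the coefficient can be too low, for example 0.57 against 0.68. Left out, they raise the maximum width from 0.39 to about 0.51.

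These figures rest on 40% pCR, on the assumed CEDM accuracies, and on the simulation's assumptions about the sizes of missed lesions. The 0.39 is not an arithmetic error; it is correct for 100 patients. Sixty is an upper bound on measurable residual lesions at 40% pCR, because Appendix C describes patients with only intravascular or intralymphatic residual cancer who are ypT0 but not pCR. With 55 measurable lesions the maximum width would be 0.53.

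**What to change.** In Section 8.3 item 3, report two Spearman correlations with pathologic size for each modality:
- **(a)** in patients with residual invasive disease at surgery, as the measure of how well imaging sizes residual tumour;
- **(b)** in all patients, with pCR and imaging complete response entered as size zero and ties given mid-ranks, labelled as reflecting pCR detection as well as sizing.

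State that a residual tumour not seen on imaging is also entered as imaging size zero in (a).

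In Section 8.2, keep 0.39 for (b). Add a maximum width of about 0.51 for (a), based on at most 60 patients at 40% pCR, and note that it is slightly wider if some patients without pCR have no measurable invasive focus.

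The cost is wording only: no new patients, visits or measurements. There are two downsides. The interval for (a) is wider, and (a) leaves out overestimation in patients with pCR, which is why (b) is kept beside it.

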### **8.3 Data Analyses**

Descriptive statistics will be produced for all patients; frequencies and percentages for categorical measures and means, medians, standard deviations, and ranges for continuous measures. The number of cancer foci identified by each imaging modality will be compared. Tumors will be categorized according to immunohistochemical approximated molecular profiles (Luminal A, Luminal B, Triple-negative and HER-2 amplified). Additional exploratory analyses will be performed as needed.

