#### **1. Sensitivity of CEDM versus mammography**

Histopathological assessment will be used as the reference standard.

For categorical measurements of tumor response (CR/PR/SD/PD or RCB0-I /RCB II /RCB III):

1. Sensitivities and specificities in predicting pCR (or RCB0) will be calculated for CEDM and mammography respectively.
2. The agreement between CEDM and mammography in categorizing tumor response (CR/PR/SD/PD or RCB0-I/ RCBII/RCBIII) will be assessed using weighed kappa.

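### Imaging size is compared with pathologic size only by Spearman correlation, which the Study Summary calls a measure of agreement; no planned statistic with an interval can show systematic mis-sizing against pathology (minor).

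*Combined protocol and SAP*

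**What the plan says.** Section 8.3, item 3, plans for size against pathology that Spearman's "rank correlation will be used to measure the association between final pathologic and imaging tumor size". The Study Summary, under Statistical Methodology, describes the same analysis differently: "Spearman rank correlation will be used to measure the agreement between final pathologic and imaging tumor size data". Its second listed objective is "To investigate the correlation accuracy of CEDM pre-operative lesion size and final pathological size, compared to mammography".

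The body uses correlation language throughout. Section 2.2.1 asks for the correlation of pre-operative CEDM size with final pathological size, section 2.4.2 names a correlative statistic, and section 8.1 speaks of correlation.

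Agreement statistics appear elsewhere, but for a different pair of measurements. Section 8.3, item 1, applies weighted kappa to "The agreement between CEDM and mammography in categorizing tumor response", and section 6.3 does the same. Item 2 says: "The agreement between CEDM and mammography in RECIST, percent change in volume and pre-surgery lesion size will be assessed using intraclass correlation (ICC".

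Section 8.3 also promises "means, medians, standard deviations, and ranges for continuous measures" and leaves room for further exploratory analyses as needed. Section 8.2 gives precision for size against pathology only for the rank correlation: "100 patients will provide 95% confidence interval of spearman rank correlation of lesion size with a width no larger than 0.39". It also states "We assume 40% prevalence of pCR".

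**The concern.** Agreement and rank association are different properties. A modality that doubles every tumour's size orders the tumours perfectly and measures none of them correctly. If a high coefficient is reported as agreement, it can be read as evidence that CEDM sizes residual tumour accurately before surgery, and that reading could be carried into the multi-institutional study that section 8.2 foresees.

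Directional error is also the kind of error that the background treats as a known weakness. Section 1.2 says mammography may underestimate the degree of response, and the text under Table 2 says MRI can underestimate residual disease. The plan commits to no interval for such an error against histopathology, which section 8.3 names as the reference standard for its accuracy analysis. It also commits to no measure of how far one patient's imaging size may lie from the pathologic size.

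**Working it through.** **1. The plan's own figure.** Section 8.2 names Fisher's transformation with a normal approximation. The interval is widest at a correlation of zero, where its width is 2·tanh(1.96/√(n−3)).
- n = 100: 2·tanh(1.96/√97) = 0.393, which reproduces the stated 0.39.
- n = 60 (100 patients less the assumed 40% pCR, taken as the approximate number with residual tumour): 2·tanh(1.96/√57) = 0.508, about 0.51.

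The stated width is correct for 100 patients. It does not describe an analysis restricted to residual tumours.

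**2. What Spearman cannot see.** Assume lognormal pathologic size with median 20 mm and log SD 0.6 (the documents give no size distribution). Let imaging size be exactly k times pathologic size. The ranks coincide, so Spearman is 1.00 for every k. The squared coefficient of variation is c = exp(0.36) − 1 = 0.433, and Lin's concordance is 2kc / [c(1 + k²) + (k − 1)²].
- k = 1.3: 1.127 / 1.256 = 0.90
- k = 1.5: 1.300 / 1.658 = 0.78
- k = 2.0: 1.733 / 3.167 = 0.55

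The same holds with measurement noise. With assumed median 15 mm, log SD 0.6 and measurement log SD 0.25, a simulation gave:

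| Imaging size | Spearman | Lin's concordance | Mean difference |
|---|---|---|---|
| Unbiased on the log scale | 0.916 | 0.90 | 0.5 mm |
| 1.5 times | 0.916 | 0.68 | 9.8 mm |
| 2 times | 0.916 | 0.47 | 19.0 mm |
| Plus 10 mm | 0.916 | 0.67 | 10.5 mm |

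**3. Whether another planned analysis fills the gap.**
- ICC and weighted kappa compare CEDM with mammography. The two can agree closely while both mis-size against pathology.
- ROC analysis of pre-surgery size is also rank-based and concerns classification of response, not error in millimetres.
- Separate descriptive means allow a crude subtraction, without a paired interval and without information on individual error.
- The clause on exploratory analyses permits an agreement analysis but names none.

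**4. Why the analysis set must be shown.** The documents give no accuracy for CEDM, so take the mammography figures in section 1.2 for predicting pCR (sensitivity 54.2%, specificity 86.3%) as a stand-in, with 40% pCR. Assume otherwise unbiased sizing, a mean size of 20·exp(0.18) = 23.9 mm, and the same size distribution for tumours seen where none remains.
- Residual tumours with imaging size zero: 60 × 0.137 = 8.2 expected.
- Tumours seen on imaging with none at pathology: 40 × 0.458 = 18.3 expected.
- Mean difference where ypT size is above zero: −0.137 × 23.9 = −3.3 mm.
- Mean difference in all patients: (0.40 × 0.458 − 0.60 × 0.137) × 23.9 = +2.4 mm.

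The sign depends on the set, although sizing itself is unbiased. The first set counts misses but not false positives.

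**5. Precision of the added analyses.** The half-width of the 95% CI for a paired mean difference is t/√n in SD units: 0.198 SD at n = 100 and 2.001/√60 = 0.258 SD at n = 60. Limits of agreement are harder. A simulation at n = 60 used the sizes of step 2, proportional error of log SD 0.3, and 9% or 13.7% of tumours missed. The usual normal-theory 95% interval for the lower limit covered the true value only about 61–63% of the time (72% with no missed tumours). The interval for the mean difference kept about 95% coverage.

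**The case against.** The strongest reply is that the operative text is consistent. The body's objective, endpoint and analysis all ask for correlation or association, and Spearman answers that question. The study calls itself exploratory and descriptive, has no formal sample size calculation, and leaves room for further analyses on data it already collects. On this view the textual error is one word in a synopsis. Most of that stands, and it is why the point is minor. What remains is that a permission is not a commitment, and that the Summary's wording claims more than the planned statistic can deliver.

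Three stronger readings are tempting, and the documents do not support them.
- A reader might infer that the coefficient will mostly repeat detection of pCR, because pCR patients would enter with size zero. The plan does not say that they enter this way, although the precision statement for 100 patients suggests it. With no sizing ability at all among residual tumours, the coefficient over all patients would be about 0.31 at the mammography accuracy. If Spearman among residual tumours seen on imaging were 0.7 (assumed), it would be 0.47 over all patients against 0.52 where ypT size is above zero. The effect is conditional and is not always inflation.
- A reader might conclude that the residual-tumour set should decide whether CEDM sizes correctly. That set is chosen on the pathology result, which is unknown before surgery, and step 4 shows that it builds in under-sizing.
- A reader might take the stated width of 0.39 as an error. It is right for 100 patients.

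**Conclusion.** The concern holds as a minor, cheap improvement plus one wrong word. The plan has no statistic with an interval that could reveal systematic mis-sizing of tumours by CEDM or mammography against pathology, and the Summary labels a rank correlation as agreement. That Spearman is blind to a uniform error is a property of ranks and needs no assumption. The size of the contrast (Spearman 1.00 against Lin's concordance of 0.90, 0.78 or 0.55) rests on the assumed lognormal sizes. The opposite signs of −3.3 mm and +2.4 mm rest on mammography accuracy standing in for CEDM, on 40% pCR and on the assumed sizes.

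It should not be inferred that the body's size objective goes unanswered or that the AUC analysis is compromised: no patient, design feature or AUC result is affected. The Summary lists the size objective as primary while section 2.2 lists it as secondary, and the CEDM dimension and post-injection time point to be paired with ypT are not named. Those are separate matters and add no weight here.

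**What to change.** 1. In the Study Summary, Statistical Methodology, replace *agreement* with *association*.
2. In section 8.3, item 3, keep Spearman. Add, for CEDM and for mammography against pathologic size, the paired mean difference with its 95% CI. Add also limits of agreement, or Lin's concordance or ICC, with bootstrap intervals or percentile-based limits, because the differences are skewed and include missed tumours. Bootstrap intervals for the limits are themselves approximate at about 60 patients, so the interval for the mean difference should carry the main statement on bias.
3. Report these for all patients, with size zero coded as zero, and for patients with ypT size above zero, side by side and with neither set deciding the conclusion. Give the number of residual tumours with imaging size zero and the number of tumours seen on imaging where ypT size is zero. State in advance that the mean difference can have opposite signs in the two sets.
4. In section 8.2, state that the maximum width of the Spearman interval is 0.39 at n = 100 and about 0.51 if about 60 patients have residual tumour.

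The cost is SAP wording and a little programming on data already collected, with no change to design or accrual. The downside is wider intervals in the residual-tumour set: up to about 0.51 for Spearman, and a half-width of about 0.26 SD for the mean difference at n = 60, against 0.20 SD at n = 100.
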